15.2 Data control

15.2.1 Electronic control of the data

The data manager or their deputy will review all data entered in the eCRF, as they arise. Queries raised will be directed to the investigators at the relevant clinical site using the dedicate tool of the eCRF or during a monitoring visit. Prior to analysis, the safety data will be checked, AEs validated and data extracted in order for the trial statisticians to run the analysis and prepare the tables.

15.2.2 Data control in the clinical site

Before starting the trial, the CMG Inserm UMR S 1136 will establish the monitoring plan that will be sent to the trial sponsor (Inserm-ANRS). The monitoring plan may be amended during the trial based on the dynamic of inclusions.

15.2.3 Participants in charge of study monitoring

Monitoring will be done by the CMG project manager from CMG Inserm UMR S 1136 mandated by the sponsor in accordance with the regulations and recommendations of Good Clinical Practice. At any time, the CRA or project manager in charge of the trial can be contacted for any questions regarding the protocol and its practical application.

15.2.4 Monitoring of the trial

An investigator meeting with at least one representative in each participating centre will be held before starting the trial. Staff from CMG Inserm UMR S 1136 in charge of trial monitoring will visit the clinical centres. The first visit will be to open the centre. This opening visit will be held before any screening in the centre. During this visit, the CMG project manager will give to investigators all documents needed for starting the trial: Protocol, Manual for the use eCRF, and all procedures. Participants (clinical centres and laboratories members) in each centre must be present during the opening visit.

All monitoring visits will be done in the centres with at least one patient included and will take place according to the monitoring plan established by the CMG Inserm UMR S 1136. The first monitoring visit will take place within the first three months after the first inclusion in the centre.

the CMG Inserm UMR S 1136 projet manager in charge of the monitoring is responsible for to validate data entered in the eCRF against the clinical records. The site principal investigator and participants, by giving consent, agree that the CMG Inserm UMR S 1136 may consult and/or copy source records (clinical notes and laboratory values) in order to do this. Such information will be treated as strictly confidential and will in no circumstances be made publicly available. The monitoring will adhere to ICH GCP guidelines.

The volume of data that will be collected allows us to plan only a control of 100% of the baseline data and 100% of the data used as endpoints in 100% of patients.

However, particular attention will be paid to the following data:

- Signed consent
- Documentation of any existing conditions or past conditions relevant to eligibility
- Dates of visits
- Laboratory results
- Grade 3 or 4 AEs and any events leading to trial treatment discontinuation
- Date of trial treatment discontinuation, date of giving up, and date of consent withdrawal

A Closing visit will take place in each of the centres in which at least one patient has been selected at the end of the trial.

15.3 Auditing

An audit can be performed at any time by persons representing the sponsor and independent from the research. Its objectives are to ensure the quality and follow-up of the research, data consistency and local regulations in force.

The sponsor's as well as the investigational products' suppliers' Quality Assurance Units (or representatives) may conduct audits at the trial site(s). Audits will include, but are not limited to, drug supply, presence of required documents, the informed consent process, and comparison of eCRFs with source documents. The investigator agrees to participate with audits conducted at a reasonable time in a reasonable manner.

Regulatory authorities worldwide may also inspect the investigator during or after the trial. The investigator should contact the sponsor immediately if this occurs, and must fully cooperate with the inspections conducted at a reasonable time in a reasonable manner.

16 STATISTICAL CONSIDERATIONS

16.1 Patients sample calculation

ANRS 163 ETRAL is a non-comparative phase II trial evaluating in HIV-1-infected patients, of at least 45 years of age, switching from a virologically suppressive boosted PI-containing regimen the capacity of a dual raltegravir/etravirine regimen to maintain the virological success as defined by the absence of 2 consecutive HIV-RNA plasma VL > 50 copies/mL within 2 to 4 weeks.

Raltegravir/etravirine will be considered acceptable if the percentage of patients in virological success at week 48 is significantly above 90 %.

Assuming a 95 % virological success rate, by including **160 individuals** and considering the strategy to be acceptable if no more than 8 individuals have virological failure; we will have a 95 % probability to discard a

combination for which efficacy is smaller than 90 % and we will select with a power of 80 % the strategy for which the efficacy is above or equal to 95 %.

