	
 - Modification of peripheral and central body fat distribution at W48 and W96 compared to D0 measured by DXA scan (Dual-energy X-Ray Absorptiometry) (DXA scan sub-study, 80 patients). - Evolution of bone mineral density measured by DXA scans at W48 and W96 compared to D0 (DXA scan sub-study, 80 patients). - To assess HIV-RNA viral load and Cmin (Minimal Drug Concentration) of raltegravir and etravirine at W48 in human male genital compartment (semen sub-study, 20 patients). - Evolution of the inflammation markers (IL-6hs, sCD14, sCD163, D-Dimers, IP-10, IgG, CRPus and insulin on frozen plasma aliquots from D0 to W48, and W96). - Evaluation of health-related quality of life with a self-assessment questionnaire at D0, W48, W96 and of the compliance with a self-assessment questionnaire at W-6/W-4, W48, W96. - 
 • Evaluation of the evolution of the cardio-vascular disease-related markers in women according to their ovarian reserve and their menopausal status - Evolution of the ovarian reserve from D0 to W48 measured by AMH on frozen aliquots - Evolution of the level of MCP1/CCL2 from D0 to W48 on frozen samples - Evaluation of the metabolic/inflammatory profile according to sex at inclusion and its evolution up to week 48 - Evaluation of metabolic profile, inflammatory, innate immune activation markers in women according to their status regarding ovarian reserve and menopausal status at inclusion and its evolution up to week 48
Methodology	Multicenter non-comparative phase II trial evaluating the capacity of the dual combination raltegravir/etravirine to maintain virological success defined as the absence of 2 consecutive plasma viral loads (VL) > 50 copies/mL within 2 to 4 weeks in virologically suppressed HIV-1 infected patients, of at least 45 years of age, switching from a boosted PI-containing regimen.
Estimated enrolment	By including 160 individuals and considering the strategy to be acceptable if at least 152 individuals maintain virological success, we will have a 95 % probability to discard a combination for which efficacy is smaller than 90 % and we will select with a power of 80 % a strategy for which the efficacy is above or equal to 95 %.

Study endpoints **Primary endpoint** Proportion of patients remaining, at week 48 on virological success defined as the absence of 2 consecutive HIV-RNA plasma VL > 50 copies/mL within 2 to 4 weeks interval.

Secondary endpoints

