16.2.2 Statistical methods

The primary endpoint is the virological success up to week 48 defined by the absence of 2 consecutive HIV-RNA plasma VL > 50 copies/mL within 2 to 4 weeks.

The therapeutic success is defined by the absence of virological failure and the absence of treatment interruption due to adverse event judged by DSMB as related to the trial treatment or procedure up to week 96.

In particular:

- Patients with 2 or more consecutive missing HIV-1 RNA plasma viral load values or lost to follow up will be considered as patients with treatment failure (failing patients).
- Patients who discontinue the treatment due to adverse event judged by DSMB as related to the trial treatment or procedure will be considered as failing patients.
- Patients who discontinued the treatment due to adverse event judged by DSMB as NOT related to the trial treatment or procedure will not be considered as failing patients.
- Patients who gave up will not be considered as failing patients.
- Patients who discontinued the trial treatment for any reason other than a virological failure or adverse event judged by DSMB as related to the trial treatment will not be considered as failing patients.
- Patients with a missing HIV-1 RNA value between 2 documented HIV-1 RNA plasma viral loads \leq 50 copies/mL will not be considered as failing patients.

Analysis of the primary endpoint will be performed on both ITT and per protocol populations. The 95% two-sided confidence interval of the percentage of patients in therapeutic success will be calculated and raltegravir/etravirine will be considered as an acceptable strategy if the lower bound is greater than 90%.

The changes in continuous endpoints will be compared in the ITT population (LOCF or other imputation method to be defined in the statistical analysis plan) using a two-sided non-parametric paired Wilcoxon test with a 5 % type I error. We will use percentage and 95 % two-sided confidence interval to describe the qualitative endpoints, their change over time will be tested a McNemar test with a 5 % type I error.

The adverse events leading to a trial treatment discontinuation and the number of patients who discontinued the trial treatment, as well as the number and nature of grade 3 and 4 adverse events will be described.

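### Sections 16.1 and 16.2.2 state the single decision rule in non-equivalent ways: the quoted 95 % does not describe the 8-failure limit, and limit and interval can disagree because no CI method is named and the limit is tied to N = 160

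*Combined protocol and SAP*

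**What the plan says.** Section 16.1 first says the regimen will be "considered acceptable if the percentage of patients in virological success at week 48 is significantly above 90" %, with no level and no side. It then gives a limit on failures and its error rate. With 160 patients and an expected success rate of 95 %, the strategy passes where "no more than 8 individuals have virological failure; we will have a 95 % probability to discard a" regimen with efficacy below 90 %; power is put at 80 % for a true rate of 95 % or more. The English synopsis (Estimated enrolment) puts the same limit as successes, "considering the strategy to be acceptable if at least 152 individuals maintain virological success", with the same 95 % and 80 %. The French synopsis repeats this.

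Section 16.2.2 gives the rule for the analysis: "The 95% two-sided confidence interval of the percentage of patients in therapeutic success will be calculated", and the strategy is acceptable if the lower bound is above 90 %. The method of calculating the interval is not named. The interval is written for therapeutic success, whereas the limit in 16.1 counts virological failures.

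Section 16.2.1 excludes patients who withdrew consent from the ITT population and excludes further patients from the per-protocol population. Section 16.2.2 analyses the primary endpoint in both. Appendix A8 reports 165 patients included.

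**The concern.** The trial has one arm and one success criterion, so that criterion should have one error level and give one answer for any result. Here it is stated as a probability of discarding (5 % one-sided), as a maximum number of failures, and as a confidence bound (2.5 % one-sided). If these are not equivalent, the verdict near the boundary depends on which statement is applied, in a non-comparative trial without blinding. With no interval named, that choice could be made after the number of failures is known.

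**Working it through.** **Inputs.** N = 160, limit of 8 failures, null success 0.90, alternative 0.95, stated 95 % probability to discard and 80 % power (16.1 and synopses). Lower bound of a two-sided 95 % CI above 90 % (16.2.2). 165 included (Appendix A8). N = 150 is an assumption, used to show a smaller analysed set.

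**Step 1: the plan's own figures.** Let X be the number of failures.
- Type I error: P(X ≤ 8 | 160, 0.10) = 0.0174, so the probability to discard is 1 − 0.0174 = 98.3 %, against the stated 95 %.
- Power: P(X ≤ 8 | 160, 0.05) = 0.593, against the stated 80 %.

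Neither figure is reproduced. The neighbouring limits do not give both: at most 9 failures has error 0.0359 and power 0.720; at most 10 has error 0.0670 and power 0.821.

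**Step 2: the level that the limit of 8 fits.** It is the largest limit with error below 0.025 (0.0174, then 0.0359 for 9). A one-sided 5 % level would allow 9. So the number in 16.1 matches the interval in 16.2.2, and the percentage in 16.1 does not.

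**Step 3: limit against interval.** The exact (Clopper-Pearson) lower bound exceeds 0.90 when P(X ≤ f | n, 0.10) is below 0.025. The Wald bound is p̂ − 1.96·√(p̂(1−p̂)/n). For 9 of 160, p̂ = 151/160 = 0.94375 and the standard error is 0.01822, so the bound is 0.94375 − 1.96 × 0.01822 = 0.908.

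| Failures / N | P(X ≤ f) at 0.10 | Exact 95 % bound | Wilson | Wald | Limit in 16.1 |
|---|---|---|---|---|---|
| 8 / 160 | 0.0174 | 90.4 % | 90.4 % | 91.6 % | accepts |
| 9 / 160 | 0.0359 | 89.6 % | 89.7 % | 90.8 % | rejects |
| 10 / 160 | 0.0670 | 88.8 % | 88.9 % | 89.999 % | rejects |
| 8 / 150 (assumed N) | 0.0307 | 89.8 % | 89.8 % | 91.1 % | accepts, if 8 is kept |
| 9 / 165 | 0.0275 | 89.9 % | 89.96 % | 91.1 % | none stated for 165 |
| 10 / 165 | 0.0527 | 89.1 % | 89.2 % | 90.3 % | none stated for 165 |

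**Step 4: where they part.**
- At N = 160, exact and Wilson intervals agree with the limit on every row. Only the Wald interval differs, at 9 failures: 16.2.2 accepts and 16.1 rejects. Exactly 9 failures has probability 12.7 % if true success is 95 %.
- At an assumed N of 150, 8 failures meets the limit but fails the exact interval. The change falls between N = 154 (P = 0.0245, bound 90.02 %) and N = 153 (P = 0.0260, bound 89.96 %).
- At N = 165, 9 failures fails by the exact interval and passes by Wald.

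**The case against.** A reader might infer that 9 failures of 160 is accepted at the 5 % level of 16.1 and rejected at the 2.5 % level of 16.2.2, each with a sentence of the protocol behind it. The documents do not support that. Section 16.1 rejects 9 in words, and both synopses repeat the limit. The exact p-value for 9 (0.036) does lie between 0.025 and 0.05, but no section writes a one-sided 5 % test as a separate rule. The sentence on significance above 90 % carries no level, and the same section goes on to give the limit of 8. The one real split at N = 160 runs the other way, with 16.2.2 accepting under a Wald interval and 16.1 rejecting. It follows that 12.7 % is not the chance of an ambiguous result in general; it is that only if a Wald interval is used.

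The sponsor can also say that the 95 % understates the true 98.3 %, so it errs on the safe side, and that 16.2.3 promises a detailed analysis plan before any analysis, where an interval method could be named. Both points are fair. They reduce the weight of the level mismatch and show that the remedy is mainly wording. They do not make the quoted 95 % a description of the written limit, they do not say what replaces 8 when N is not 160, and nothing in the document supplied names the method.

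**Conclusion.** The point holds as a failure of equivalence, not as two competing thresholds at 9 failures. The nominal levels differ (5 % against 2.5 % one-sided), and the stated probability to discard is not that of the limit beside it (98.3 %, type I error 1.7 %). At N = 160 the limit and an exact or Wilson interval give the same verdict for 8, 9 and 10 failures. Opposite verdicts arise in two situations that the text leaves open: a Wald interval, or an analysed N other than 160. The second is likely, since 165 were included and 16.2.1 removes patients from both analysis populations.

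The figures assume independent binomial outcomes with every analysed patient classified as success or failure. The analysed N is not given, and 150 is illustrative. The same sentence also overstates power: 59 % for the written limit, not 80 %. That is a separate fault, but the sentence cannot be corrected without it.

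**What to change.** 1. In 16.2.2, make one rule decide at whatever N is analysed: acceptable if the lower bound of the two-sided 95 % Clopper-Pearson interval exceeds 90 % (one-sided alpha 2.5 %).
2. Apply that interval to the primary endpoint, virological success at week 48, in place of therapeutic success.
3. In 16.1 and both synopses, give at most 8 failures (at least 152 successes) as the equivalent of this rule at N = 160 only.
4. In the same places, replace the 95 % probability to discard by at least 97.5 % (exact 98.3 %), and the 80 % power by about 59 % at a true success rate of 95 %.
5. In 16.1, attach the level and side to the sentence on being significantly above 90 %.

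The cost is wording: no further patients or data. The limit of 8 at N = 160 does not change, and 9 of 160 was already a rejection under 16.1. The downside is that the stated power becomes less favourable. At this level an exact test first reaches 80 % power at 231 patients (at most 14 failures).

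### The 80 % power does not follow from the stated rule: with 160 patients and at most 8 failures, power at 95 % true success is 59 %, and a 90 % regimen is discarded with probability 98.3 %, not 95 %

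*Combined protocol and SAP*

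**What the plan says.** Section 16.1 starts from a hypothesised rate ("Assuming a 95 % virological success rate") and 160 patients. It sets the rule by "considering the strategy to be acceptable if no more than 8 individuals have virological failure". Two operating characteristics are then claimed for that rule. On the unfavourable side, "we will have a 95 % probability to discard a" "combination for which efficacy is smaller than 90" %. On the favourable side, "we will select with a power of 80 % the strategy for which the efficacy is above or equal to 95" %.

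The English synopsis (Estimated enrolment) makes the same claim with the equivalent limit on successes: "By including 160 individuals and considering the strategy to be acceptable if at least 152 individuals maintain virological success". Since 160 − 152 = 8, this is the same rule. The French synopsis repeats it with the same four numbers.

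The analysis in 16.2.2 is set out as an interval: "The 95% two-sided confidence interval of the percentage of patients in therapeutic success will be calculated", and the strategy is acceptable if the lower bound is above 90 %. The interval method is not named. No sample-size formula and no allowance for dropout is given anywhere.

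**The concern.** The limit is placed at the expected number of failures under the hoped-for rate: 160 × 0.05 = 8. A count falls at or below its own expectation only a little more than half the time, so a rule set there cannot have 80 % power.

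The sidedness does not line up either. A 95 % probability of discarding describes a one-sided 5 % test, whereas 8 failures of 160 is the limit that a two-sided 95 % interval (one-sided 2.5 %) produces under most methods.

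This is the only justification of the sample size, and it concerns the trial's one primary decision. A reader who believes the power is 80 % will take a failure to pass as fairly strong evidence against the strategy. If the power is really 59 %, that inference is much weaker.

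**Working it through.** **Inputs**, all from 16.1 and 16.2.2: n = 160; accept if the number of failures X ≤ 8; unacceptable success 90 % (failure 0.10); hoped-for success 95 % (failure 0.05); claimed discard probability 95 %; claimed power 80 %; analysis by two-sided 95 % interval with lower bound above 90 %.

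**Step 1. The stated rule, exact binomial.**

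- Power at 95 %: P(X ≤ 8 | 160, 0.05) = Σₖ₌₀⁸ C(160,k) 0.05ᵏ 0.95¹⁶⁰⁻ᵏ = 0.593.
- False acceptance at 90 %: P(X ≤ 8 | 160, 0.10) = 0.0174, so the discard probability is 1 − 0.0174 = 0.983.

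The plan's 80 % and 95 % are not reproduced.

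**Step 2. Approximations with the same limit.** The variance under 95 % is 160 × 0.05 × 0.95 = 7.6.

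- Normal: Φ((8 − 8)/√7.6) = 50.0 %.
- Normal with continuity correction: Φ(0.5/√7.6) = 57.2 %.
- Poisson with mean 8: 59.3 %.

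**Step 3. Other failure limits at n = 160.**

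| Failures allowed | Accept at 90 % | Discard at 90 % | Power at 95 % | Exact 95 % lower bound at the limit |
|---|---|---|---|---|
| 8 | 1.7 % | 98.3 % | 59.3 % | 90.4 % |
| 9 | 3.6 % | 96.4 % | 72.0 % | 89.6 % |
| 10 | 6.7 % | 93.3 % | 82.1 % | 88.8 % |

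No limit gives a discard probability of at least 95 % together with power of at least 80 %.

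**Step 4. Formulas that ignore the limit.** These were tried in case the 80 % came from a textbook formula.

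| Method | One-sided 5 % | One-sided 2.5 % |
|---|---|---|
| Normal, null and alternative variances | 73.8 % | 58.1 % |
| Normal, null variance only | 67.8 % | 55.9 % |
| Normal, alternative variance only | 89.6 % | 82.7 % |
| Arcsine | 78.5 % | 68.2 % |

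For example, the first entry is Φ((0.05√160 − 1.645√0.09)/√0.0475) = Φ(0.638) = 73.8 %. Two entries come near 80 %: arcsine at 5 % and alternative variance at 2.5 %. Neither is tied to 8 failures. The arcsine result corresponds to a limit of about 10 failures, where false acceptance is 6.7 %.

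**Step 5. The interval rule of 16.2.2 at n = 160.** Clopper-Pearson, Wilson, Agresti-Coull and Jeffreys intervals all need at least 152 successes, so power is again 59.3 %. The Wald interval needs 151, with power 72.0 %.

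**Step 6. What would give 80 %.**

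- With the limit of 8, power reaches 80 % at a true success rate of about 96.0 % (at exactly 96 % it is 80.7 %).
- The smallest exact designs with at least 80 % power for 90 % against 95 % are n = 179 with at most 11 failures (one-sided 5 %) and n = 231 with at most 14 failures (one-sided 2.5 %).

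**Step 7. The number enrolled.** Appendix A8 reports 165 patients. If the limit stays at 8, which is also what the Clopper-Pearson and Wilson intervals allow, power at 95 % is 55.7 %.

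**The case against.** The arithmetic for the printed rule is not in dispute. The objections concern how much of it matters.

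- **The 95 % is met as a minimum.** Discarding with probability 98.3 % is stricter than promised, so patients are not put at risk by that figure. This stands. The harmful error is the power. But 98.3 % is still not the figure the rule gives, and the gap shows that the limit works at one-sided 2.5 % while the text describes 5 %.
- **The interval method is not named, so there is no single true power once 16.2.2 governs.** This stands for the interval rule. At 165 patients, Jeffreys allows 9 failures (68.8 %) and Wald allows 10 (79.5 %), so the 55.7 % holds only where the limit is 8. It does not rescue 16.1, which fixes the limit at 8 of 160.
- **The trial is well advanced.** This version is dated January 2018, and Appendix A8 says that patients are enrolled and first results are favourable, so a negative result may no longer be in prospect. That reduces the practical consequence. It does not make the stated power correct, and the final report would carry it forward.
- **Rewording does not restore 80 % power.** True. It makes the description honest; it does not enlarge the trial.

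**Conclusion.** The concern holds. For the rule printed in 16.1 and both synopses, power at 95 % true success is 59.3 %, about 21 points below the stated 80 %. False acceptance at 90 % is 1.7 % rather than 5 %. A regimen at the hoped-for rate would be judged not acceptable 40.7 % of the time, twice the implied 20 %.

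This rests on independent patients with a common success probability and all 160 evaluable, both implicit in the plan's own calculation. The decision limit itself is sound: it agrees with the 16.2.2 criterion under the exact and Wilson intervals. What is wrong is the description of how the rule performs.

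**What to change.** In 16.1 and in the English and French synopses, replace the two claimed probabilities with, for example: *With 160 patients and at most 8 failures, the probability of accepting a regimen with 90 % efficacy is 1.7 %; power is 59 % at 95 % true success and about 80 % at 96 %.* State the one-sided level as 2.5 %, so that it matches the two-sided 95 % interval in 16.2.2, and name the interval method there (Clopper-Pearson or Wilson both reproduce the limit of 8 of 160).

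Because first results were already known in this version, mark the change as a dated correction of the operating characteristics, not as the original design basis.

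Do not simply relax the limit to 10 failures to recover the 80 %: false acceptance would be 6.7 %, and the exact lower bound at the limit would be 88.8 %, below the 90 % that 16.2.2 requires.

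The cost is wording in three places and a less favourable stated power. Sample size, failure limit and planned analysis are unchanged, and no extra patients are needed for the correction. Reaching 80 % at 95 % would have needed 179 patients (one-sided 5 %) or 231 (one-sided 2.5 %).
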